### 1.2 Secondary Hypotheses

Secondary hypotheses are as follows:

1. Theracurmin can increase the frequency of ALS reversals (defined by an improvement of 4 or more points in the ALSFRS-R over the course of 6 months) from 2-5% (observed spontaneously) to at least 10%.
2. Theracurmin can alter the fecal microbiome in patients with ALS.
3. The fecal microbiome of patients with ALS is significantly different from matched control subjects.
4. The fecal microbiome of patients with ALS is significantly different between subgroups with differing clinical features including sporadic vs. familial, anatomical location of symptom onset, and rate of progression as measured on the ASLFRS-R.
5. The novel features of this pilot trial will be associated with improved participant enrollment compared to prior more traditional ALS trials where enrollment is 2 participants per site per month.
6. The novel features of this pilot trial will be associated with improved participant retention compared to prior more traditional ALS trials where the dropout rate is 22% at 12 months.
7. The novel features of this pilot trial will be associated with improved participant compliance compared to prior more traditional ALS trials.

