### 2.3 Success of Previous Hybrid Virtual/Remote Trial

We previously conducted an open-label, single-center, hybrid-virtual 12-month trial of Lunasin for patients with ALS (6). This single-center trial featured broad inclusion criteria, historical controls, mostly virtual data collection, and real-time results. Participants measured their ALSFRS-R score, weight and perceived efficacy, and recorded these monthly on PatientsLikeMe (PLM; an online platform described section 2.7). ALSFRS-R decline was compared to historical controls. For each enrolled participant, PLM identified 3 historical controls matched according to pre-treatment ALSFRS-R progression, as in their previous Lithium study (7). We had 90% power to detect 50% slowing in decline of ALSFRS-R scores.

Although there were no significant differences in ALSFRS-R ( $p=0.99$ ) between study participants and historical controls, the study's outcomes suggested that there is utility and internal validity in a virtual trial model. Enrollment rate was 9.1 participants per site per month, which is the fastest rate of any ALS trial in history. As in most ALS trials, our 50 participants were primarily white (94%) males (58%), mean age of 60, limb onset disease (82%), taking riluzole (60%). However, our participants had longer disease duration than those in most trials, and several had non-invasive ventilation, PEG and/or tracheostomy, which are traditional exclusion criteria. This trial population was therefore more representative of the population seen in ALS clinics. In spite of enrolling patients with longer and more advanced disease, the survivor retention rate was 84%, while the survivor retention rate in traditional ALS trials is 78% (5).

We also looked at the accuracy of patient recorded ALSFRS-R and weight measurements. Lin's concordance (C) showed high agreement between coordinator and participant derived ALSFRS-R and weight respectively at month 1 ( $C=0.9939, 0.9947$ ) and month 12 visits ( $C=0.9428, 0.9905$ ). These results suggest that participant recorded ALSFRS-R scores and weight are sufficiently accurate to be used in a clinical trial.

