Compliance with study protocol (assessed by the percentage of patients who logged onto PLM every month and entered at least 2 of the 3 key outcomes) was 88% or greater for each of the first 6 months, but then began to decline, eventually reaching only 55% at 12 months. This suggests that a 6 month virtual trial design may allow for high compliance throughout the entire study duration.

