### **3.3.6 Retention**

Retention will be assessed by looking at the dropout rate at 6 months (the percentage of surviving enrolled patients who complete the Month 6 Visit). A previous meta-analysis of traditional clinical trials showed the mean ALS participant dropout rate to be 22% at 12 months (5). Our previous virtual trial with Lunasin had a dropout rate of 16% at 12 months (6).

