## **3.4 Study Schedule**

Following informed consent and screening, enrollment visit activities will commence and Therarcurmin treatment will be started. Treatment and all study activities will end at month 6. Participants will be required to make 4 video/telephone visits with the Duke study team (enrollment, weeks 1, 2, and 3). Participants will not be required to make any physical visits to Duke. At months 2-6, participants will make “Internet PLM visits” by measuring their own ALSFRS-R score and weight and height, and logging onto the PLM website to record it as well as perceived efficacy, perceived side effects, perceived compliance, changes in concomitant medications and Thrive questionnaires. Participants will be reminded to log into their PLM profile and record the above-mentioned data points via email and text reminders from PLM. The study coordinator will call/video participants at enrollment, weeks, 1, 2, 3 and for training and any time afterward when participants have not entered data for 2 weeks beyond expected entries. The call script for such communications can be found in Appendix I.

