### **4.1.2 *Primary Hypothesis and Sample Size***

For the primary hypothesis, we will run a t-test comparing the ALSFRS-R progression rate in our participants to a group of matched historical controls identified from the PatientsLikeMe community. This type of analysis has previously been used to look for treatment effects in

patients with ALS taking lithium (7), dexpramipexole and various forms of sodium chlorite (29) and lunasin (6). We made the following assumptions to calculate a sample size requirement for this analysis:

1. The mean ALS-FRS progression in 12 months is 11 points (rate of ~0.9 points/month) and the standard deviation at 12 months is ~8 ALS-FRS points (estimates based on unpublished data from PatientsLikeMe.)
2. The effect size we are looking for is to halve the mean progression rate
3. The treatment is not having a harmful effect (allows us to use a one-tailed comparison)
4. There is a 5% chance of seeing an effect this big by chance alone
5. We desire a 90% chance of finding an effect this big, assuming it is real
6. There will be a dropout rate of 15% over 6 months. We had a 16% survivor drop-out rate over 12 months in our prior Lunasin trial (6).

Based on these assumptions we will again need to enroll 50 participants (and compare them to 50 matched historical controls).

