#### **4.1.5 Retention**

To determine whether participant retention in this study is greater than in studies with more traditional designs we will compare our dropout rate (percentage of living enrolled participants that complete the Month 6 Visit) to the mean ALS participant dropout rate of 22% at 12 months (5) using a chi-squared test.

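### The retention test sets dropout at Month 6 against a 22% benchmark measured at 12 months, a mismatch that very likely favours this trial

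*Combined protocol and SAP*

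**What the plan says.** Hypothesis 6 in section 1.2 expects the trial's new features to bring "improved participant retention compared to prior more traditional ALS trials where the dropout rate is 22% at 12 months". Section 3.3.6 sets this trial's measure as the "dropout rate at 6 months (the percentage of surviving enrolled patients who complete the Month 6 Visit"). Section 4.1.5 then specifies a chi-squared test of the "dropout rate (percentage of living enrolled participants that complete the Month 6 Visit) to the mean ALS participant dropout rate of 22% at 12 months". It gives no significance level or sidedness, and it does not say whether 22% is a fixed value or an estimate with its own sample size.

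Section 3.4 fixes the length of follow-up: "Treatment and all study activities will end at month 6". No 12-month value can therefore be observed. No section converts the benchmark to 6 months, takes a 6-month benchmark, or names the difference in time point as a limitation.

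Both rates are among survivors. Section 2.3 reports for the earlier virtual trial that "the survivor retention rate was 84%, while the survivor retention rate in traditional ALS trials is 78" per cent. Section 3.3.6 gives the same results as 16% and 22% dropout at 12 months.

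**The concern.** Six months of losses are set against twelve months of losses. A trial that loses participants at the same pace as traditional trials would be expected to show a lower figure simply because it stops earlier, and the planned test would credit the difference to the design. Retention is one of the trial's main claims for its remote model, so a favourable result is likely to be cited.

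A smaller wording error sits in the same sentences. Sections 3.3.6 and 4.1.5 call the percentage who complete the Month 6 Visit a dropout rate. The paired figures in sections 2.3 and 3.3.6 (84% and 78% retention, 16% and 22% dropout) show that the complement is meant, and that meaning is used below.

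**Working it through.** The plan states no sample size, power or expected result for this test, so there is no figure of its own to reproduce.

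**Inputs from the documents.** Benchmark: 22% at 12 months (sections 1.2, 3.3.6, 4.1.5). Time point of this trial: month 6 (3.3.6, 3.4). Enrolment: 50 (3.5).

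**Assumptions not in the documents.** Constant dropout hazard in traditional trials; deaths ignored in the conversion; one-sample test against a fixed 22%, two-sided at 5%; 42 to 50 participants alive at month 6.

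**Step 1: put the benchmark on a 6-month scale.** 1 − √(1 − 0.22) = 1 − √0.78 = 0.117, or 11.7%.

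**Step 2: find when the test declares better retention.** With x dropouts among n, z = (x/n − 0.22) / √(0.22 × 0.78 / n), significant at z ≤ −1.96. At n = 50, x = 5 gives z = −2.05 and x = 6 gives z = −1.71, so 5 or fewer dropouts is significant. With a continuity correction (|x − 11| reduced by 0.5), x = 5 gives 1.88 and x = 4 gives 2.22 in absolute value, so the cut-off is 4 or fewer.

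**Step 3: chance of that result if retention is only benchmark-like.** Exact binomial with true 6-month dropout of 11.7%:

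| Living participants | Uncorrected | Continuity-corrected |
|---|---|---|
| 50 | 46% | 29% |
| 45 | 38% | 21% |
| 42 | 26% | 26% |
| Range over 42 to 50 | 26% to 48% | 21% to 36% |

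If true 6-month dropout were 22%, the same cut-offs would be met in 1.0% to 2.7% of trials uncorrected and 0.6% to 1.6% corrected.

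**Step 4: vary the timing of dropout (n = 50).** True 6-month dropout is 22% times the share of 12-month dropout that occurs by month 6:

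| Share by month 6 | True 6-month dropout | Uncorrected | Corrected |
|---|---|---|---|
| 40% | 8.8% | 72% | 55% |
| 60% | 13.2% | 34% | 19% |
| 80% | 17.6% | 11% | 5% |
| 100% | 22% | 2% | 1% |

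**Step 5: what a matched comparison could show.** At n = 50, an exact two-sided test against 11.7% gives p = 0.026 with 1 dropout and p = 0.119 with 2. Significantly better retention therefore needs 0 or 1 dropouts, which has a 28% chance even if true 6-month dropout were 5%. In the other direction, 11 or more dropouts would be significantly worse (p = 0.043).

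**The case against.** The strongest objection is that the direction is not proved. It is tempting to argue that cumulative dropout cannot fall, so the bias is certain. That does not hold for a rate among the living: a dropout who later dies leaves both numerator and denominator. With invented numbers, 20 dropouts among 100 living at month 6 is 20%. If 12 of those dropouts and 10 others die by month 12 and 5 more people drop out, the rate is 13/78 = 16.7%. This stands, and the direction should be called very likely. Nothing in the documents suggests such a pattern, and section 2.2 describes study burdens that grow heavier as disability advances.

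A second objection is that a 6-month duration may itself be one of the new features. Section 2.3 says of it: "This suggests that a 6 month virtual trial design may allow for high compliance throughout the entire study duration". The plan does not define the features, so this reading is open. But that sentence concerns compliance with data entry, not dropout, and the test still could not separate shorter follow-up from remote conduct.

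Third, the size is driven by assumptions. This stands: Step 4 runs from 72% to 1%, and section 4.1.5 does not fix the form of the test.

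Fourth, this is the sixth of seven secondary hypotheses in an open-label pilot. Both time points are printed openly, and the earlier virtual trial supplies a like-for-like comparison ("Our previous virtual trial with Lunasin had a dropout rate of 16% at 12 months", against 22%). This limits the consequence but does not repair the test for the present trial.

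A reader might also infer that the sponsor itself expects worse retention than the benchmark, because section 4.1.2 assumes "There will be a dropout rate of 15% over 6 months" and 1 − 0.85² = 27.8% at 12 months under constant hazard. The documents do not support that inference. The 15% is a sample-size allowance, it stands beside 16% over 12 months in the earlier trial, and the plan does not say whether it counts deaths.

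**Conclusion.** The point holds: the planned test can credit the design with better retention merely because follow-up is shorter. The time mismatch very likely favours this trial; the two exceptions are almost no losses in months 7 to 12 of traditional trials, or deaths among earlier dropouts that offset those losses. Under the constant-hazard illustration, the chance of wrongly declaring improvement is about 21% to 48%. That range is one case among several and not an estimate for this trial.

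A reader might go further and conclude that the retention result as a whole is biased in the trial's favour. The documents do not support that. The trial is widely inclusive and the earlier one enrolled patients with more advanced disease, which may raise dropout, so the net bias is unknown. The wording slip over dropout and completion needs correcting but adds no weight. The primary analysis, the sample size and safety are untouched. The point should be fixed, and the change is cheap.

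**What to change.** - In sections 3.3.6 and 4.1.5, define dropout as 100% minus the percentage of living enrolled participants who complete the Month 6 Visit, and report it with an exact 95% confidence interval.
- Remove the chi-squared test against 22% at 12 months as the basis for claiming better retention.
- Compare only with a 6-month benchmark. Use the 6-month value from the cited retention meta-analysis if it is available. Otherwise use a converted value descriptively: 11.7% under constant hazard, shown with a range for dropout timing (for example 8.8% to 22% if 40% to 100% of the 12-month dropout falls by month 6), and labelled as an assumption that ignores deaths.
- Amend Hypothesis 6 to 6-month retention, and state that the effect of shorter duration cannot be separated from the other design features.

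Keeping the 22% figure in the report with a plain statement of the mismatch would also be honest, provided that no claim of improvement rests on it.

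The cost is wording in three sections and no new data. The benchmark becomes less favourable and, without a published 6-month figure, rests partly on assumption. As Step 5 shows, the trial can estimate 6-month retention but is unlikely to prove improvement.

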#### **4.1.6 Microbiome Analyses**

We will compare saliva and stool microbiome samples between patients with ALS and healthy controls at every sampling point. We will compare the changes in the saliva and stool microbiome over time in patients with ALS on Theracurmin to the changes observed in untreated healthy controls. We will compare the enrollment saliva and stool microbiome across patients with different ALS origins (sporadic versus familial), onset regions (limb versus bulbar) and ALSFRS-R progression rates.

Raw, 16S microbiome sequencing data will undergo processing & strict quality control using the Qiime2 pipeline (31). Dada2 (32) will be used to infer and quantify amplicon sequence variants (ASVs). Taxonomy information will be assigned to the ASVs using the q2-feature-classifier (33) against the SILVA 132 database (34). Initial analyses of the data will focus on associations between the diversity of the microflora environment to ALS patients relative to the control samples as well as between the different forms of ALS. We will employ four different metrics for calculating within-sample diversity (alpha diversities: Faith's phylogenetic diversity, Shannon index, Pielou's evenness, and the total number of ASVs) and four different metrics for calculating between-sample diversities (beta diversities: Bray-Curtis dissimilarity, Jaccard dissimilarity, UniFrac, and weighted UniFrac). To identify associations between alpha diversity metrics and ALS, we will employ linear mixed-effects models with household as a random effect. Beta diversity indices will also be evaluated using mixed-effect modeling using the *vegan* package from the R statistical programming environment. The *PhyloSeq* (35) package will be employed to test for differential abundance of individual taxa between ALS patients and the control samples. In brief, raw ASV counts will be agglomerated in Family, Genus, and Species level data before being normalized by the 'poscounts' function from DESeq2 (36). Negative binomial linear models will then be used to identify differential abundance of microflora at the varied taxonomic ranks. Performing all analyses in a linear model framework will allow us to control for potential cofactors such as patient antibiotics usage, age, and gender. The false discovery rate will be used to control for multiple hypothesis testing.

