### **3 DESIGN & PROCEDURES:**

#### **3.1 Design Overview**

This will be a 6-month, widely inclusive, largely remote/virtual, single-center, open-label pilot trial utilizing a historical control group. Following informed consent and screening, participants will take the intervention (see section 3.2.1) for 6-months. Treatment with the intervention Theracurmin HP and all study outcome measures and labs are being performed exclusively for research purposes. Collected data includes ALSFRS-R, fecal sample microbiome sampling, adverse events, and concomitant medications. Participants will be asked to register for an account on PLM with the help of the study coordinator. User IDs associated with their PLM account will be recorded by the study coordinator and shared with study staff at PLM. When registering, participants will have the opportunity to review PLM's terms and conditions (Appendix A) as well as their privacy policy (Appendix B). After the baseline video/telephone visit, participants will be asked to enter the following data: weight and height, Theracurmin treatment evaluations (Appendix C), ALSFRS-R score (Appendix D) and Thrive Questionnaires (Appendix E). Participants will be given the following study documents and materials shipped to their home:

A PLM bag (Appendix F) including:

1. Welcome letter (Appendix G)
2. Study One-Sheet (Appendix H)
3. Study drug
4. Microbiome kits
5. PatientsLikeMe gifts

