### **3.3.3 Microbiome Sequencing**

The microbiome of study participants will be analyzed in saliva and stool samples at enrollment, week 4 and month 6 visits. Participants will be sent collection kits with which they will collect saliva and fecal samples and send by mail to Duke University for further analysis at each timepoint. Research personnel will deidentify the samples of any personally identifiable information (PII) and subsequently submit them to the Duke Microbiome Core (<https://genome.duke.edu/cores-and-services/microbiome-shared-resource>) for sample processing and preparation for biospecimens for long term archiving at the Duke University BioBank. The Duke Microbiome Core will perform DNA extraction, sequencing library preparation, and 16S rRNA sequencing on the Illumina MiSeq platform. Data analysis of the deidentified microbiome sequencing data will be conducted in collaboration with the Duke University Microbiome Center (DMC). Data will be compared within subjects with ALS to assess possible changes over the length of the study and identify microbial correlates of disease progression. Fecal microbiome data at enrollment, week 4 and month 6 will also be compared to data from healthy control participants from the same household as participants with ALS.

In addition, our collaborator [name] at the Duke Department of Molecular Genetics and Microbiology, will perform metagenomic analysis of deidentified selected fecal samples from patients that positively respond to Theracurmin to achieve strain level identification of microbes positively and negatively associated with improved outcomes. His group will also culture selected anaerobes (eg. *Akkermansia muciniphila*) that have been linked to ALS severity for further genetic and phenotypic characterization.

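### Section 4.1.6: only pre-dose enrollment samples can test whether ALS differs from controls, and post-dose contrasts cannot separate Theracurmin from ALS course

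*Combined protocol and SAP*

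**What the plan says.** Section 1.2 lists two separate microbiome hypotheses that matter here. Hypothesis 2 is that Theracurmin changes the fecal microbiome in ALS. Hypothesis 3 reads: "The fecal microbiome of patients with ALS is significantly different from matched control subjects". It names no time point.

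The analysis in section 4.1.6 opens by comparing saliva and stool samples "between patients with ALS and healthy controls at every sampling point". Section 3.3.3 agrees: "Fecal microbiome data at enrollment, week 4 and month 6 will also be compared to data from healthy control participants". Section 3.5.3 repeats the same three visits.

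For the drug effect, section 4.1.6 compares the changes over time "in patients with ALS on Theracurmin to the changes observed in untreated healthy controls". Section 3.3.3 adds a within-subject comparison among the ALS participants.

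Section 3.1 describes a "single-center, open-label pilot trial utilizing a historical control group" in which "participants will take the intervention (see section 3.2.1) for 6-months". Table 1 (section 3.4.5) marks enrollment as the start of the intervention and month 6 as its end. The historical controls of sections 4.1.1 and 4.1.2 serve the ALSFRS-R comparison only and give no samples.

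**The concern.** Hypothesis 3 is about the disease. After enrollment, the two groups differ in disease and also in treatment. A drug effect on the microbiome could then be reported as an ALS difference, or a normalising drug effect could hide a real one. The plan takes this possibility seriously itself: section 2.6.1 says the curcumin formulation altered the fecal microbiome in mice, and hopes for a more favorable profile in ALS.

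Hypothesis 2 has the opposite problem. Healthy household members have no ALS course. If diet, feeding route or other medication changes as ALS advances and the microbiome shifts with it, that shift would count as a Theracurmin effect.

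Without a stated rule, support for hypothesis 3 could be drawn from any of three visits, two of which do not measure what the hypothesis says.

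**Working it through.** The plan gives no sample size, power or effect size for the microbiome analyses, so there is no figure to reproduce. The check is whether the planned groups and visits can separate the quantities in question.

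**Inputs.** Two sampled groups: treated ALS and untreated household controls (sections 3.1, 3.5.3, 4.1.6). Three visits: enrollment, week 4, month 6 (section 3.3.3, Tables 1 and 2).

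**Group means.** Let m be the control mean at enrollment, b(t) the change shared by both groups, D the disease difference at enrollment, C(t) the ALS-specific change since enrollment, and T(t) the drug effect. At a pre-dose enrollment sample b, C and T are all zero.

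- Control mean at visit t: m + b(t)
- ALS mean at visit t: m + b(t) + D + C(t) + T(t)

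**What each planned contrast measures.**

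| Contrast | Enrollment, pre-dose | Week 4 or month 6 |
|---|---|---|
| ALS minus control | D | D + C(t) + T(t) |
| Change in ALS minus change in control | n/a | C(t) + T(t) |
| Change within ALS | n/a | b(t) + C(t) + T(t) |

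Only the first column isolates D. No row isolates T(t).

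**Count of unknowns.** There are 2 groups × 3 visits = 6 cell means. There are 8 parameters: m, b(4), b(6), D, C(4), C(6), T(4), T(6). The design matrix has rank 6, and the columns for C and T are identical at week 4 and again at month 6. Drug and ALS course are fully aliased at both visits. Adding an untreated ALS group sampled at the same visits would give 9 cells and rank 8, so all 8 parameters could be estimated.

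**Can the named models help?** Section 4.1.6 gives a household random effect and names antibiotics, age and gender as possible cofactors. None of these distinguishes C from T, because every sampled ALS participant is treated.

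**Is enrollment drug-free?** Section 3.1 puts study drug and microbiome kits in the same shipped bag, and Table 1 starts the intervention at enrollment. No instruction says that the sample comes before the first dose.

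**Illustration of size, on assumed effects.** Take one metric, a paired t-test, two-sided 5%, no FDR adjustment, and no true disease difference or ALS course (D = C = 0). With noncentrality d × √n and n − 1 degrees of freedom, 80% power needs:

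- n = 50 complete pairs: d = 0.404 SD of the paired difference
- n = 42 pairs (50 × 0.85 = 42.5, borrowing the 15% dropout of section 4.1.2): d = 0.443

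An unpaired comparison with 42 to 50 per group gives a significant ALS-control difference with probability of about 15–17% for a drug effect of 0.2 SD, 63–70% for 0.5 SD and 96–98% for 0.8 SD. These figures show what would happen under each assumed effect. They do not predict the effect.

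**The case against.** The strongest reply is that the plan hides nothing. Section 4.1.6 openly calls one group treated and the other untreated, and it never says that the week 4 and month 6 contrasts test hypothesis 3. Asking whether treated ALS moves toward or away from controls is a legitimate question given section 2.6.1. The enrollment contrast is already planned. The healthy comparator is not the only one for hypothesis 2, because section 3.3.3 also plans within-subject change. These are secondary aims of an open-label pilot.

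Much of this stands. The later contrasts are worth reporting, and the primary ALSFRS-R analysis is untouched. But the silence on hypothesis 3 matters: the same paragraph of section 4.1.6 limits the subgroup comparisons to enrollment samples, and it sets no such limit for ALS versus controls. The within-subject comparison removes D but leaves C(t) and T(t) together.

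A reader might infer that three visits inflate the type I error for hypothesis 3 to 1 − 0.95³ = 14.3%. The documents do not support that figure. Section 4.1.6 applies false discovery rate control, although it does not define the family, and the visits are correlated because the same people are sampled. Nor would FDR control cure confounding, which is the actual point.

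A reader might also infer that week 4 is nearly clean, because little ALSFRS-R decline is expected by then. That assumes microbiome drift follows ALSFRS-R decline, which no section says. The drug effect may also be smaller at week 4, and the aliasing is the same at both visits.

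**Conclusion.** The point holds for secondary hypotheses 2 and 3. As written, the week 4 and month 6 ALS-control contrasts cannot test hypothesis 3. Enrollment can, provided that the sample precedes the first dose, which the plan does not yet secure. For hypothesis 2, neither planned comparison separates drug from ALS course at either later visit. That is a limit of the single-arm design, and analysis wording cannot remove it.

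The structural result (rank 6 against 8 parameters) needs only the facts that every sampled ALS participant is treated and that no control has ALS. The size of the bias is unknown. The values of about 0.40 SD at 50 pairs and 0.44 SD at 42 pairs rest on complete pairs, a single metric and no FDR adjustment. The plan uses mixed and negative binomial models, and section 3.5.3 only aims for one control per household.

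It would go too far to infer that the enrollment samples are known to be contaminated, or that the later samples have no use. The documents leave sample order open, and the later contrasts remain informative as descriptions.

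**What to change.** In section 4.1.6, with a matching line in section 3.3.3:

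1. State that hypothesis 3 is tested on enrollment samples only, and that these are collected before the first dose of study drug. Put the sample-order instruction in the kit materials and record the sample and first-dose dates.
2. Label the week 4 and month 6 ALS-control contrasts as treated ALS versus untreated control, exploratory.
3. Report change in ALS at both week 4 and month 6, within subjects and against controls, as drug plus disease course, with no claim that Theracurmin alone caused it.

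The cost is a few sentences, one collection instruction and a more modest conclusion for hypothesis 2. No extra participants or samples are needed. Separating drug from ALS course would need samples from untreated ALS patients or repeated samples in a pre-treatment run-in. That is a different design and is not requested here.

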## 3.5 Participants

Primary participants will be patients with ALS (PALS) who are cared for by [name], or who contact our site inquiring about this study. 50 participants will be enrolled.

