### **3.5.3     *Control Subjects***

In addition to the 50 primary participants described above, we will seek to enroll 50 healthy control participants. We will attempt to enroll one control subject from each enrolled primary participant's home, preferably a spouse or partner of similar age if possible. We plan to use this data to compare the control participants to the ALS participants at baseline, week 4 and month 6. We will not conduct further follow-up or collect additional samples with the control subjects. There are no specific inclusion or exclusion criteria for control subjects except living in the same household and free of any neurodegenerative disease. This is an observational only study for the control subjects that constitutes minimal risk for the control subjects.

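### The alpha-diversity mixed model has a household effect but no participant effect, so a joint model of the repeated visits would lose power for the planned comparison of change between ALS participants and controls

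*Combined protocol and SAP*

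**What the plan says.** Sampling is repeated in both groups. Section 3.3.3 says: "The microbiome of study participants will be analyzed in saliva and stool samples at enrollment, week 4 and month 6 visits". Section 3.5.3 plans to "compare the control participants to the ALS participants at baseline, week 4 and month 6", and Table 2 schedules control samples at enrollment, week 4 and month 6.

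The design is paired by home. Section 3.5 says "50 participants will be enrolled". Section 3.5.3 adds that "we will seek to enroll 50 healthy control participants", and on their source: "We will attempt to enroll one control subject from each enrolled primary" participant's home. A complete household therefore gives 2 people x 3 visits = 6 samples per body site.

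Section 4.1.6 plans two kinds of comparison between ALS participants and controls:

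- By visit: "We will compare saliva and stool microbiome samples between patients with ALS and healthy controls at every sampling point".
- Over time: "We will compare the changes in the saliva and stool microbiome over time in patients with ALS on Theracurmin" with the changes in untreated healthy controls.

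For alpha diversity the stated model is: "we will employ linear mixed-effects models with household as a random effect". Beta diversity is also to be analysed by mixed models, but no random effect is named. The negative binomial models for individual taxa mention none. The section does not say whether the visits go into one model, into a model per visit, or into change scores.

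**The concern.** A comparison of change needs at least two samples per person. The only random effect that the plan names groups samples by home, not by person. Put the three visits into that model and the six samples from a home become exchangeable apart from the fixed effects. Stable differences between the two housemates then have nowhere to go but the residual.

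This matters most for the group difference in change, which bears on secondary hypothesis 2 (Theracurmin alters the microbiome). Each person is their own control there, so stable person-to-person variance should cancel. A residual that still contains it makes the test conservative and hides real change. Contrasts between ALS participants and controls at a given visit, which bear on secondary hypothesis 3, err the other way if they are read from the same joint model, because person variance is counted only in part. Control of the false discovery rate does not repair p-values that come from wrong standard errors.

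**Working it through.** The plan gives no sample size, power or variance for the microbiome analyses, so there is no figure of its own to reproduce. The check is a variance-components calculation.

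**Inputs from the plan.** One ALS participant and one control per home, up to 50 homes (sections 3.5 and 3.5.3); three visits per person (sections 3.3.3 and 3.5.3); household as the only random effect (section 4.1.6).

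**Assumptions.** Complete pairs, all three visits, constant variances. Household variance is 20% of the total. Person variance P is 20%, 40% or 60%, and residual variance E is the rest (60%, 40% or 20%). The within-household person ICC, P/(P+E), is then 0.25, 0.50 or 0.75.

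**Step 1: the residual of a household-only model.** Six samples leave five degrees of freedom within a home. One compares the two people's means and has mean square E + 3P. Four are within person and have mean square E. The model pools them:

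(E + 3P + 4E)/5 = E + 0.6P.

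**Step 2: ratio of the model's standard error to the true one.** The number of homes cancels.

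- Difference in change between two visits: the true variance per pair is 4E and the model uses 4(E + 0.6P). Ratio = sqrt((E + 0.6P)/E) = sqrt(1 + 0.6P/E).
- Group difference at one visit, read from the joint model: ratio = sqrt((E + 0.6P)/(E + P)).
- Group difference averaged over visits: ratio = sqrt((E + 0.6P)/(E + 3P)).

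**Step 3: consequences (normal approximation, two-sided 5%).** For a ratio r, type I error is 2[1 - Phi(1.96r)]. An effect with 80% power under the right model is 2.802 true standard errors, so power under the household-only model is Phi(2.802 - 1.96r).

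| Person / residual share | E + 0.6P | Change: ratio | Power, from 80% | One visit from joint model: ratio, type I | Averaged over visits: ratio, type I |
|---|---|---|---|---|---|
| 20% / 60% | 0.72 | sqrt(0.72/0.60) = 1.10 | 74% | sqrt(0.72/0.80) = 0.95, 6% | sqrt(0.72/1.20) = 0.77, 13% |
| 40% / 40% | 0.64 | sqrt(0.64/0.40) = 1.26 | 63% | sqrt(0.64/0.80) = 0.89, 8% | sqrt(0.64/1.60) = 0.63, 22% |
| 60% / 20% | 0.56 | sqrt(0.56/0.20) = 1.67 | 32% | sqrt(0.56/0.80) = 0.84, 10% | sqrt(0.56/2.00) = 0.53, 30% |

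Over an ICC range of 0.2 to 0.8, the type I error of a visit-specific contrast from the joint model runs from about 6% to 11%.

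**Step 4: a single visit analysed alone.** Each person gives one sample and household is the right grouping. Simulation of 50 pairs gave a standard-error ratio of 0.98 and a type I error of 5.9%, close to nominal.

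**The case against.** The strongest reply is that section 4.1.6 leaves the data structure open and does not commit to a wrong model. The sentence with the household effect concerns associations of alpha diversity with ALS, and the group comparison is planned at each sampling point. Fitted one visit at a time, that model is sound. Change could be analysed as one score per person with a household effect, and no error would arise. Section 3.3.3 also plans a comparison within ALS participants over the study. With one patient per home, the household intercept is normally the participant intercept in that analysis, so it is handled correctly. All of this stands, and it makes the point conditional.

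The figures also describe the fully balanced case. The plan only seeks 50 controls, and section 4.1.2 allows for 15% dropout. In a home without a control, household and participant coincide and the problem disappears. That stands too: incomplete pairing would soften the figures.

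A reader might infer more: that the microbiome standard errors are wrong in both directions whatever is done, and that hypothesis 3 will be tested with a type I error of 13% to 30%. The documents do not support this. Those rates belong to a contrast averaged over visits, which the plan does not state. Nor does the loss of power extend to all of hypothesis 2, since the within-ALS comparison escapes it.

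What the objection does not remove is the comparison of change between ALS participants and controls. The plan commits to it, it needs more than one visit, and the only random-effect structure stated does not suit a joint model of it.

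**Conclusion.** The point holds on one condition: that several visits from both ALS participants and controls enter one alpha-diversity model with household as the only random effect. The standard error of the group difference in change is then too wide for any positive person variance. The excess is about 10%, 26% or 67%, and 80% power falls to about 74%, 63% or 32%, under the assumed variance shares and complete pairs. Visit-specific group contrasts from that model are mildly anti-conservative, with a type I error of about 6% to 11% for an ICC of 0.2 to 0.8.

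This is more than missing detail, because a better model for a planned comparison is available from the same data. It should be corrected before the data are analysed. Its reach is limited to secondary microbiome hypotheses; the primary ALSFRS-R analysis is unaffected.

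**What to change.** In section 4.1.6, for alpha-diversity models that use more than one visit, specify random intercepts for household and for participant nested within household, with fixed effects for group, visit and group-by-visit. Alternatively, state that each visit is modelled separately and that change is analysed as one score per person with a household effect. Household alone can stay for single-visit comparisons.

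Beta diversity and the negative binomial taxon models cannot simply take the same line. State for each a suitable method that respects the pairing and the repeated samples: for example, permutations restricted within participant or household, or one visit at a time with the pairing accounted for.

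The cost is one extra variance component, a few sentences in the plan and a little more analysis work. No new data or visits are needed.
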